5. ENDPOINTS

5.1 PRIMARY ENDPOINTS

The primary endpoint for this study is a safety endpoint:

- Time to first International Society of Thrombosis and Haemostasis (ISTH) Major Bleeding Event (MBE) or Clinically Relevant Non-Major Bleeding Event (CRNMBE). Please refer to the CTP for the ISTH criteria.

The primary endpoint will be adjudicated by an Independent Adjudication Committee (IAC). Details of adjudication criteria can be found in the Adjudication Charter.

5.2 SECONDARY ENDPOINTS

5.2.1 Key secondary endpoints

Not applicable.

5.2.2 (Other) Secondary endpoints

The other secondary endpoints of efficacy are (all time to first event endpoints):

1. Composite endpoints of:

[figure not shown]
[figure not shown]
- DTE and unplanned revascularisation by PCI/CABG.
(DTE = all death, Myocardial Infarction (MI), stroke/Systemic Embolism (SE))
- DTE

2. Individual outcome events:

- All death (and the following sub-categories separately)
 - Cardiovascular death
 - Non-cardiovascular death
 - Undetermined
- MI
- Stroke
- SE
- Stent thrombosis (definite)

3. Composite endpoint of death + MI + stroke
4. Unplanned revascularisation by Percutaneous Coronary Intervention (PCI)/Coronary Artery Bypass Graft (CABG)

All secondary endpoints will be adjudicated by an IAC. Details of adjudication criteria can be found in the Adjudication Charter.

6. GENERAL ANALYSIS DEFINITIONS

6.1 TREATMENTS

The following treatment periods based on actual start and stop dates/times of randomised study drug administration are defined:

- Screening: date of informed consent to date of randomisation.
- Post-randomisation: Date of randomisation to time-point of first intake (date and time) of randomised study drug.
- On-treatment (ignoring temporary interruptions): first intake (date and time) of randomised study drug to last intake (date and time) of randomised study drug. The REP of 6 days will be added to the end of this period. Intermittent off-treatment periods will be ignored in cases of any temporary interruptions in study medication.
- Post-treatment: End of on-treatment period (including the REP) until date of trial completion. This is the date given on the termination (TERM) page of the electronic Case Report Form (eCRF).
- Post-study: day after date of trial completion onwards.

The REP is the time period after the last administration of trial medication when measurable drug levels or PD effects are still likely to be present. Events occurring in the REP are handled as occurring on-treatment (for the Treated Set). The REP is defined as 6 days after last intake of trial medication. Data from the post-study period will only be listed.

For rules on censoring, refer to [Section 7.4](#).

Despite the trial being open label, all activities conducted by the trial team will be performed in a blinded manner (where possible) until database lock (DBL). For example, data tabulations and listings will be presented using dummy treatment group information instead of actual treatment group allocations.

6.2 IMPORTANT PROTOCOL VIOLATIONS

The following table defines the different categories of Important Protocol Violations (IPVs). The final column describes which IPVs will be used to exclude patients from the different patient analysis sets. In this study, patients are either excluded from “All” analysis sets, the Per Protocol analysis Set (PPS), the Full Analysis Set (FAS) or “None” of the analysis sets. Refer to [Section 6.3](#) for more details. Most IPVs will be identified by the trial team prior to DBL, where possible in a blinded manner. Some programmatically-identified IPVs (e.g. treatment switching) will need to be identified after DBL.

Table 6.2: 1 Important protocol violations

Category/ Code	Description	Example/Comment	Excluded from
A	Entrance criteria not met		
A1.1	Male or female patients aged ≥ 18 years or ≥ 20 years in Japan.	Inclusion criterion 1 not met	PPS
A1.2	Patients with NVAf that have been receiving oral anticoagulant (OAC) treatment (either with warfarin, another Vitamin K Antagonist (VKA) or other novel oral anticoagulant), or were treatment naïve prior to PCI. Atrial Fibrillation (AF) may be paroxysmal, persistent or permanent, but must not be secondary to a reversible disorder such as MI, pulmonary embolism, recent surgery, pericarditis or thyrotoxicosis	Inclusion criterion 2 not met	PPS
A1.3	Patients presenting with: 
 • An Acute Coronary Syndrome (ACS) [ST elevation MI (STEMI), NSTEMI or unstable angina (UA)] that was successfully treated by PCI and stenting [either Bare Metal Stent (BMS) or Drug Eluting Stent (DES)] Or • Stable Coronary Artery Disease (CAD) with at least one lesion eligible for PCI that was successfully treated by elective PCI and stenting (either BMS or DES) 	Inclusion criterion 3 not met	PPS
A2.1	Patients with a mechanical or biological heart valve prosthesis	Exclusion criterion 1 met	PPS
A2.2	Cardiogenic shock during current hospitalisation	Exclusion criterion 2 met	PPS
A2.3	Patients who have used fibrinolytic agents within 24 hours of randomisation that, in the opinion of the Investigator, will put the patient at high risk of bleeding	Exclusion criterion 3 met	PPS
A2.4	Stroke within 1 month prior to screening visit (Additionally in Japan: a haemorrhagic stroke, 6 months prior to administration of study treatment)	Exclusion criterion 4 met	PPS
A2.5	Patients, who in the opinion of the Investigator, have had major surgery within the month prior to screening	Exclusion criterion 5 met. Nature and timing of surgery to be reviewed at Report Planning Meeting (RPM).	None
A2.6	Patient has received an organ transplant or is on a waiting list for an organ transplant	Exclusion criterion 6 met	PPS
A2.7	History of intraocular, spinal, retroperitoneal or a traumatic intra-articular bleeding unless the causative factor has been permanently eliminated or repaired (e.g. by surgery)	Exclusion criterion 7 met	PPS

Table 6.2: 1 (continued) Important protocol violations

Category/ Code	Description	Example/Comment	Excluded from
A2.8	Gastrointestinal (GI) haemorrhage within one month prior to screening, unless, in the opinion of the Investigator, the cause has been permanently eliminated (e.g. by surgery)	Exclusion criterion 8 met	PPS
A2.9	Major bleeding episode (reduction in the haemoglobin level of at least 2g/dL, transfusion of at least two units ¹ of blood, or symptomatic bleeding in a critical area or organ) including life-threatening bleeding episode (symptomatic intracranial bleeding, bleeding with a decrease in the haemoglobin level of at least 5g/dL or bleeding requiring transfusion of at least 4 units ² of blood or inotropic agents or necessitating surgery) in one month prior to screening visit	Exclusion criterion 9 met	PPS
A2.10	Haemorrhagic disorder or bleeding diathesis (e.g. von Willebrand disease, haemophilia A or B or other hereditary bleeding disorder, history of spontaneous intra-articular bleeding, history of prolonged bleeding after surgery/intervention)	Exclusion criterion 10 met	PPS
A2.11	Anaemia (haemoglobin <10g/dL) or thrombocytopenia including heparin-induced thrombocytopenia (platelet count <100 × 10 ⁹ /L) at screening (Visit 1)	Exclusion criterion 11 met	PPS
A2.12	Severe renal impairment (estimated CrCl calculated by Cockcroft-Gault equation) <30mL/min at screening (Visit 1)	Exclusion criterion 12 met	PPS
A2.13	Active liver disease as indicated by at least one of the following: 
 • Prior and persistent alanine aminotransferase (ALT) or Aspartate transaminase (AST) or alkaline phosphatase (AP) >3 × upper limit of normal (ULN) • Known active hepatitis C • Known active hepatitis B • Known active hepatitis A 	Exclusion criterion 13 met	PPS
A2.14	Recent malignancy or radiation therapy (≤6 months) unless, in the opinion of the Investigator, the estimated life expectancy is greater than 36 months	Exclusion criterion 14 met	PPS
A2.15	Need for continued treatment with systemic ketoconazole, itraconazole, posaconazole, cyclosporine, tacrolimus, dronedarone, rifampicin, phenytoin, carbamazepine or St. John's Wort.	Exclusion criterion 15 met	PPS

¹ Equivalent to 4.5 units in Japan

² Equivalent to 9 units in Japan

Table 6.2: 1 (continued) Important protocol violations

Category/ Code	Description	Example/Comment	Excluded from
A2.16	Patients who, in the Investigator's opinion, need continuous treatment with Non-Steroidal Anti-Inflammatory Drugs (NSAIDs)	Exclusion criterion 16 met	PPS
A2.17	Patients with a known allergy to dabigatran etexilate or to the excipients used for the capsule of the drug	Exclusion criterion 17 met	PPS
A2.18	Patients with a known allergy to warfarin tablets or to the excipients	Exclusion criterion 18 met	PPS
A2.19	Patients who, in the Investigator's opinion, should not be treated with OAC	Exclusion criterion 19 met	PPS
A2.20	Patients with a contraindication to clopidogrel, ticagrelor or aspirin (ASA)	Exclusion criterion 20 met	PPS
A2.21	Pre-menopausal women (last menstruation \leq 1 year prior to screening) who: 
 • Are pregnant or breast feeding or • Are not surgically sterile or • Are of child bearing potential and not practising two acceptable methods of birth control, or do not plan to continue practising an acceptable method of birth control throughout the trial. Acceptable methods of birth control are oral or parenteral (patch, injection, implant) hormonal contraception which has been used continuously for at least one month prior to the first dose of study medication, intrauterine device or intrauterine system, double-barrier method of contraception (condom and occlusive cap or condom and spermicidal agent), male sterilisation and complete sexual abstinence (if acceptable by local authorities). Periodic abstinence is not an acceptable method of contraception. 	Exclusion criterion 21 met. Pregnant patients will be excluded from the PPS.	None
A2.22	Patients who have participated in another trial with an investigational drug or device within the past 30 days preceding the screening visit or are participating in another trial (patients participating in an observational study only will not be excluded)	Exclusion criterion 22 met	PPS
A2.23	Patients not willing or able to comply with the protocol requirements or considered unreliable by the Investigator concerning the requirements for follow-up during the study and/or compliance with study drug administration, who have a life expectancy less than the expected duration of the trial due to concomitant disease, or who have any condition which in the opinion of the Investigator, would not allow safe participation in the study (e.g. drug addiction, alcohol abuse).	Exclusion criterion 23 met	PPS

Table 6.2: 1 (continued) Important protocol violations

Category/ Code	Description	Example/Comment	Excluded from
B	Informed consent		
B1	Informed consent not given	Inclusion Criterion 4	All
B2	Informed consent given too late or the dates of the investigator's and patient's signatures do not match		None
B3	Informed consent withdrawn	Only applies from the date at which consent is withdrawn.	All
C	Trial medication and randomization		
C1	Incorrect trial medication taken	Medication kit assigned not matching treatment patient was randomised to (e.g. patient randomized to warfarin-TAT but received 110mg DE-DAT)	PPS
C2	Randomisation order not followed	e.g. forced randomization, mis-stratification	PPS
C3	Non-compliance	
Compliance <80% or >120% over the course of the study for dabigatran patients (determined on a visit-wise basis), or time in therapeutic target range for warfarin patients <45% (also on a visit-wise basis). See Section 7.3 for details on compliance calculations. Patients will be flagged if they exhibit non-compliance for two consecutive visits or more (for both dabigatran and warfarin patients).
 
Non-compliance caused by temporary interruption of treatment due to a procedure or a drop in CrCl to less than 30mL/min should not be classified as a protocol violation.
	PPS, but only from start of non-compliance onwards
C4	Trial medication taken at the wrong time	First dose of study drug not administered at the correct time (should be between 6 hours after sheath removal and up to 120 hours post PCI)	PPS
D	Concomitant medication		

Table 6.2: 1 (continued) Important protocol violations

Category/ Code	Description	Example/Comment	Excluded from
D2.1	Prohibited medication use	
The following treatments should not be taken during the active treatment period of the trial (at least one on-treatment use, unless otherwise stated):
 
 1. Treatment with ticlopidine or prasugrel 2. Fibrinolytic agents (see Section 4.2.1.4 of the protocol for exceptions) 3. GPIIb/IIIa antagonists (e.g. abciximab, tirofiban) 4. Treatment with systemic ketoconazole, itraconazole, posaconazole, cyclosporine, tacrolimus, dronedarone and rifampicin, phenytoin, carbamazepine or St. John's Wort (only applicable to patients randomised to dabigatran etexilate) 5a. Dipyridamole (although it is allowed for exceptional cases based on CTP Section, 4.2.1.4; for the PPS analyses all patients with on-treatment use will be excluded), 5b. Other oral anticoagulants (e.g. VKAs) 
Commercial NOACs (dabigatran, rivaroxaban, apixaban and edoxaban):
 
Warfarin Patients: At the end of the treatment, flag patients with more than 2 days of overlap of warfarin and commercial NOAC + flag any days of overlap during the treatment period (except for washout of previous treatment/titration at study start (see IPV C4))
 
Dabigatran patients: At the end of treatment, flag patients with more than 1 day of overlap of dabigatran and commercial NOAC + flag any days of overlap during the treatment period (except for washout of previous treatment/titration at study start (see IPV C4))
 
Commercial VKAs:
 
Dabigatran patients: At the end of treatment, flag patients with more than 5 days of overlap of dabigatran and commercial VKA +flag any days of overlap during the treatment period (except for washout of previous treatment/titration at study start (see IPV C4))
 
Warfarin patients: At the end of treatment, flag patients with more than 1 day of overlap of warfarin and commercial VKA. +flag any days of overlap during the treatment period (except for washout of previous treatment/titration at study start (see IPV C4))
 
 6. ASA in the first 12 months for all patients – except for in the first month for warfarin patients with a BMS or the first three months for warfarin patients with a DES (consecutive use of more than 14 days) 	PPS

Table 6.2: 1 (continued) Important protocol violations

Category/ Code	Description	Example/Comment	Excluded from
D2.2	Prohibited use of heparin	Any on-treatment use of heparin where no medical indication is given.	PPS
D3.1	Mandatory medication not taken per protocol (ASA)	ASA not taken for the first month for warfarin patients with a BMS or for the first three months for patients with a DES as indicated on the Trial Medication Compliance eCRF page (exclude if at least one visit is ticked "No").	PPS, but only from start of non-compliance onwards
D3.2	Mandatory medication not taken per protocol (clopidogrel/ticagrelor)	Clopidogrel/ticagrelor non-compliance during the first 12 months of treatment as indicated on the Trial Medication Compliance eCRF page (exclude if at least one visit is ticked "No").	PPS, but only from start of non-compliance onwards
G	Trial Specific Protocol Violations		
G1	Patient not withdrawn from treatment if CrCl drops to <30mL/min at two different occasions during the trial	As per study protocol, this only applies to patients randomised to dabigatran etexilate.	PPS

KEY: PPS – Per Protocol Set

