3.3.1 Main diagnosis for study entry

3.3.2 Inclusion criteria

The patient must meet all the inclusion criteria:

1. Male or female patients aged ≥ 18 years
2. Patients with NVAF that have been receiving oral anticoagulant treatment (either with warfarin, another VKA or other novel oral anticoagulant), or were treatment naïve prior to PCI. AF may be paroxysmal, persistent or permanent, and not secondary to a

Proprietary confidential information.

© 2016 Boehringer Ingelheim International GmbH or one or more of its affiliated companies. All rights reserved.

This document may not - in full or in part - be passed on, reproduced, published or otherwise used without prior written permission.

reversible disorder such as MI, pulmonary embolism, recent surgery, pericarditis or thyrotoxicosis, unless long term oral anticoagulation is planned

3. Patient presenting with:

- An ACS (STEMI, NonSTEMI [NSTEMI] or unstable angina [UA]) that was successfully¹ treated by PCI and stenting (either BMS or DES)

Or

- Stable Coronary Artery Disease with at least one lesion eligible for PCI that was successfully¹ treated by elective² PCI and stenting (either BMS or DES)

4. The patient must be able to give informed consent in accordance with International Conference on Harmonisation (ICH) Good Clinical Practice (GCP) guidelines and local legislation and/or regulations.

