Description of change	
Inclusion 2
 
Patients with NVAf that have been receiving oral anticoagulant treatment (either with warfarin, another VKA or other novel oral anticoagulant), or were treatment naïve prior to PCI. AF may be paroxysmal, persistent or permanent, but must not be secondary to a reversible disorder such as MI, pulmonary embolism, recent surgery, pericarditis or thyrotoxicosis
 
Has been changed to:
 
Patients with NVAf that have been receiving oral anticoagulant treatment (either with warfarin, another VKA or other novel oral anticoagulant), or were treatment naïve prior to PCI. AF may be paroxysmal, persistent or permanent, and not

Proprietary confidential information.

© 2016 Boehringer Ingelheim International GmbH or one or more of its affiliated companies. All rights reserved.

This document may not - in full or in part - be passed on, reproduced, published or otherwise used without prior written permission.

Number of global amendment	1
	secondary to a reversible disorder such as MI, pulmonary embolism, recent surgery, pericarditis or thyrotoxicosis, unless long term oral anticoagulation is planned
Rationale for change	To allow inclusion of patients who are a candidate for long term oral anticoagulation.
Section to be changed	3.3.3 Exclusion Criteria
Description of change	
Footnote added to exclusion 13:
 
Active liver disease as indicated by at least one of the following:
 
 • Prior and persistent alanine aminotransferase (ALT) or Aspartate transaminase (AST) or alkaline phosphatase (AP) >3 × upper limit of normal (ULN)¹ • Known active hepatitis C • Known active hepatitis B • Known active hepatitis A 
¹ Clinical judgement of whether ALT/AST enzyme elevation is due to active liver disease or due to ACS, should be made by the Investigator following evaluation of the clinical characteristics of the patient and the laboratory findings.

Rationale for change	To provide clarification to exclusion criterion 14 in relation to active liver disease.
Section to be changed	3.3.3 Exclusion Criteria

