10. HISTORY TABLE

Table 10: 1 History table

Version	Date (DD-Mmm-YY)	Author	Sections changed	Brief description of change
1	14-May-14		None	This is the first TSAP without any modification
Final	9-Jun-17		All	Updated due to global protocol amendments 1,2 and 3.

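### SAP violation A1.2 omits the long-term-anticoagulation exception in current inclusion criterion 2; applied as written, it would remove eligible patients from the per-protocol set

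*SAP*

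**What the plan says.** **Protocol.** Section 3.3.2, inclusion criterion 2, requires that AF not be secondary to a reversible disorder, followed by the exception "unless long term oral anticoagulation is planned". Amendment 1, dated 16 September 2015, introduced that clause (Protocol Section 11). The rationale given there is "To allow inclusion of patients who are a candidate for long term oral anticoagulation".

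**SAP.** Row A1.2 of Table 6.2:1 accepts any of three AF patterns, subject to this restriction: "but must not be secondary to a reversible disorder such as MI, pulmonary embolism, recent surgery, pericarditis or thyrotoxicosis". It has no exception. The comment column reads "Inclusion criterion 2 not met", and the last column assigns exclusion from the PPS.

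**Status of the SAP.** The final version is dated 9 June 2017. Its reference list cites protocol version 4, and its history table gives the reason for the revision as "Updated due to global protocol amendments 1,2 and 3".

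**Role of the PPS.** SAP Section 6.3 admits treated patients who have no important protocol violation (IPV). Table 6.3:1 uses the PPS for the primary endpoint and for demographic and baseline data only. The FAS is the main set and the others serve as sensitivity analyses. PPS analyses may be omitted if fewer than 10% of the treated set are excluded.

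**The concern.** A violation row should restate the criterion it polices. This one restates a superseded form. A patient can satisfy inclusion criterion 2 of the protocol the SAP cites and still match the A1.2 description of someone who fails it.

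If the description were followed, correctly enrolled patients would be missing from a pre-specified robustness analysis of the primary endpoint and would be counted as entry violators in the report. A1.2 also removes a patient entirely. Rows C3, D3.1 and D3.2, by contrast, exclude only from the start of non-compliance onwards.

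**Working it through.** The plan gives no figure on this point, so the check is a comparison of texts.

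**1. The two current rules, by type of patient**

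| Patient | Protocol v4, criterion 2 | SAP A1.2 description |
|---|---|---|
| AF not secondary to a reversible disorder | meets | no violation |
| AF secondary to a reversible disorder, long-term anticoagulation planned | meets | violation, out of PPS |
| AF secondary to a reversible disorder, long-term anticoagulation not planned | fails | violation, out of PPS |

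They disagree only in the middle row, which is the group the exception covers.

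**2. Where the SAP wording comes from.** The amendment log gives the superseded text as "AF may be paroxysmal, persistent or permanent, but must not be secondary to a reversible disorder such as MI" and so on, which is the A1.2 wording. The log only explains the origin. The conflict itself lies between protocol version 4 and the final SAP, both current.

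**3. Timing.** Amendment 1 is dated 16 September 2015 and the final SAP 9 June 2017, almost 21 months later. The SAP was not written before the change.

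**4. Oversight or choice.** Other rows of Table 6.2:1 carry Amendment 1. A2.15 no longer lists cytotoxic or myelosuppressive therapy, and C4 uses the 120-hour window for the first dose. SAP Section 4, which lists changes to the planned analysis, mentions no intention to exclude the exception group. An incomplete update is the natural explanation.

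**5. What depends on A1.2.** Three outputs do: the PPS analysis of the primary endpoint (SAP Sections 6.3 and 7.4), the PPS demographic and baseline tables (Table 6.3:1), and the frequencies of patients with IPVs (SAP Section 7). The primary analysis is on the FAS (SAP Section 7.4), so the FAS result and the six-step hierarchy that follows from it do not use A1.2.

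**6. The 10% rule.** Assume the treated set equals the planned 2502 patients. The threshold is then 0.10 × 2502 = 250.2, about 250 patients excluded for any reason. The number falling in the middle row of the table is not in the documents, so its share of that total cannot be computed. The direction is clear: extra exclusions make it more likely, not less, that the PPS analysis is run.

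**The case against.** The strongest reply is that nobody need be misclassified. The comment column refers to inclusion criterion 2, which the protocol defines, and SAP Section 3 assumes familiarity with the protocol and its amendments. The description column is not always a complete rule: row A1.3 leaves out the protocol's footnoted definition of a successful PCI. SAP Section 6.2 says the trial team identifies most violations before database lock, and Section 6.3 has set membership decided, where possible, before lock and minuted. The only programmatic example given is treatment switching. A team coding against version 4 would not flag these patients.

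Much of this stands. Exclusion is conditional on the description being applied. It does not remove the defect, because Section 6.2 presents the table as defining the violation categories, and A1.2's description and comment now point to different rules. A1.3 leaves a detail out, whereas A1.2 states a bar that the criterion no longer contains.

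A reader might also infer more than the documents support:

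- **That every patient with AF secondary to a reversible disorder is wrongly flagged.** This holds only for those with planned long-term anticoagulation who were enrolled under the amended criterion. Before Amendment 1 took effect, the bar was the criterion in force.
- **That Amendment 1 was written for AF after MI.** The stated rationale is candidacy for long-term anticoagulation. MI is one of five disorders named, and the trial also enrols elective PCI for stable disease.
- **That the 10% rule adds harm.** Omission below 10% is discretionary, and extra flags push towards running the analysis.

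**Conclusion.** The point holds as an inconsistency between two current documents. The A1.2 description carries the wording of criterion 2 from before Amendment 1, in an SAP that says it was updated for that amendment. Applied as written, it would exclude eligible patients from the PPS and inflate the violation counts.

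The size is minor. The PPS is a sensitivity set, the FAS primary analysis and the hierarchy are untouched, and the number of patients concerned is unknown and may be zero. The mismatch in wording is certain. The exclusion of patients is not, since it rests on the assumption that coders follow the description and not the criterion named beside it. The documents do not show that any patient was in fact misclassified.

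**What to change.** Rewrite the A1.2 description to match current inclusion criterion 2, including the exception "unless long term oral anticoagulation is planned". Add one sentence to SAP Section 6.2 stating that each patient's eligibility is judged against the protocol version in force at that patient's enrolment. Replacing the text without that sentence would excuse genuine violators enrolled before Amendment 1 took effect. Protocol Section 11 marks Amendment 1 for implementation only after ethics and authority approval, so the date in force is the local implementation date, not 16 September 2015.

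The cost is one table row, one sentence and a list of local implementation dates. Design, endpoints, the primary analysis and the sample size stay as they are. If A1.2 flags have already been set, those for patients enrolled under the amended criterion should be rechecked and the outcome recorded in the report planning or database lock minutes.
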